1 week follow-up Assessment (Follow-up) will be obtained via REDCap based text message or email (or phone call from research staff) at 1 week (+/- 4 days) of patient's ED discharge for both arms. To maintain assessor blinding, any 1-week phone calls (if needed) will be conducted by a research staff (SC or RA) who did not interact with the patient during their study participation in the ED.

- Pain Assessment (Post) using a 0-10 NRS
- Anxiety scores using a 0-10 NRS
- Satisfaction and will be measured through brief questions. All participants will be asked to answer;
 - “How satisfied are you with how your pain was managed during your ED visit” on the 5-point Likert scale.
 - “Overall how satisfied are you with your treatment during your ED visit?” on the same Likert Scale.
- Pain medications utilized from ED discharge to 1 week after discharge will be obtained from patients via phone call, email, or text messaging via the secure REDCap electronic data collection tool.

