6.2.5 Completion/Final Evaluation

Four Week Follow-Up Assessment Visit

4 week follow-up Assessment (Follow-up) will be obtained via REDCap based text message or email (or phone call from research staff) at 4 week (+/- 4 days) of patient's ED discharge for both arms. To maintain assessor blinding, any 4-week phone calls (if needed) will be conducted by a research staff (SC or RA) who did not interact with the patient during their study participation in the ED.

- Pain Assessment (Post) using a 0-10 NRS
- Anxiety scores using a 0-10 NRS
- Satisfaction and will be measured through brief questions. All participants will be asked to

answer:

- "How satisfied are you with how your pain was managed during your ED visit" on the 5-point Likert scale.
- "Overall how satisfied are you with your treatment during your ED visit?" on the same Likert Scale.
- Pain medications utilized from ED Discharge to 4 weeks after discharge will be obtained from patients via phone call, email, or text messaging via the secure REDCap electronic data collection tool.

Early Termination

The study doctor or the sponsor can stop a subject's participation at any time without their consent for the following reasons:

- If it appears to be medically harmful to them;
- If they fail to follow directions for participating in the study;
- If it is discovered that they do not meet the study requirements;
- If the study is canceled; or
- For administrative reasons, including competitive enrollment (e.g. the target number of subjects has entered the study.)
- If the patient's clinical condition worsens emergently as determined by the ED physician/clinician.

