1-week and 4-week follow-up data (PROs, pain medication/opioid use) will be collected either directly from the participant through the electronic data collection tool (via text message prompt) or collected on paper survey and entered by a member of the research team if the follow-up is completed over the phone. As above, all 1-week and 4-week contacts will be conducted by a research staff (SC or RA) who did not interact with the patient during their study participation in the ED.

All electronic data will be kept in password protected databases behind an electronic firewall at sites and then securely sent to the Einstein Coordinating Center and maintained on password protected PCs by a designated data manager. Data in hard copy form will be stored in locked file cabinets within a secure, badge-access location at each site. Upon completion of study enrollment, members of the study team will verify the information contained within the database. After answering all queries in the database, the information contained will be locked and exported for analysis. Both the source (electronic data collection) data and exported databases will be stored as required by the respective rules and regulations (e.g., HIPAA authorizations will be maintained for at least six years).

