2. Please rate your anxiety, **right now**, on a scale of 0 to 10, where 0 is no anxiety, and 10 is the worst anxiety imaginable.

0 1 2 3 4 5 6 7 8 9 10

SECTION 3 – Satisfaction

3. How satisfied are you with how your pain was managed during your ED visit?

- a. Very Unsatisfied
- b. Somewhat Unsatisfied
- c. Neutral
- d. Somewhat Satisfied
- e. Very Satisfied

4. Overall how satisfied are you with your treatment during your ED visit?

- a. Very Unsatisfied
- b. Somewhat Unsatisfied
- c. Neutral
- d. Somewhat Satisfied
- e. Very Satisfied

FOLLOW UP FORM for 1 week F/U AND 4 week F/U – To be completed by everyone, ideally from an automatic text and email generated by REDCap. If not by email, coordinator will text or phone the participant and enter the answers into REDCap.

Instructions: Below are some questions that ask you to remember what happened since your discharge from the Emergency Room on [er_visit_date].

Section 1-Medications

1. Since your discharge from the Emergency Room on [er_visit_date], have you taken any pain medications for your medical condition?
 - a. Yes
 - b. No
 - c. I don't know
 - i. If yes, “were these medications prescribed by a medical professional?

Check all that apply:

1. Yes, by Emergency room provider

2. Yes, by Primary Care Provider
 3. Yes, by Other medical professional [FREE TEXT]
 4. No
 5. I don't know
2. [branched from 1.a.i.1] Since your discharge, which pain medication(s) was prescribed by your EMERGENCY ROOM PROVIDER? Please select all that apply. (radio):
 1. Oxycodone (OxyContin, Oxecta, Roxicodone)
 2. Oxycodone / Acetaminophen (Percocet, Endocet, Roxicet)
 3. Oxycodone and Naloxone (Targiniq ER)
 4. Fentanyl (Actiq, Duragesic, Fentora)
 5. Methadone (Dolophine, Methadose)
 6. Morphine (Astramorph, Avinza, Kadian, MS Contin, Ora-Morth SR)
 7. Codeine
 8. Tylenol with codeine
 9. Hydrocodone (Hysingla ER, Zohydro ER)
 10. Hydrocodone / Acetaminophen (Lorcet, Lortab, Norco, Vicodin)
 11. Hydromorphone (Dilaudid, Exalgo)
 12. Aspirin
 13. Tylenol
 14. Ibuprofen
 15. Naproxen
 16. Celebrex
 17. Other: [FREE TEXT]
 18. Do not know
 19. Decline to answer
- a. How often have you taken these pain medication(s) on average?
 1. Several times a day
 2. Once a day
 3. Several times a week
 4. Once a week
 5. Several times per month
 6. Once per month
 7. Can't recall
 8. Decline to answer
 9. Other: [FREE TEXT]

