6. Morphine (Astramorph, Avinza, Kadian, MS Contin, Ora-Morth SR)
7. Codeine
8. Tylenol with codeine
9. Hydrocodone (Hysingla ER, Zohydro ER)
10. Hydrocodone / Acetaminophen (Lorcet, Lortab, Norco, Vicodin)
11. Hydromorphone (Dilaudid, Exalgo)
12. Aspirin
13. Tylenol
14. Ibuprofen
15. Naproxen
16. Celebrex
17. Other: [FREE TEXT]
18. Do not know

19. Decline to answer

a. How often have you taken these pain medication(s) on average?

1. Several times a day
2. Once a day
3. Several times a week
4. Once a week
5. Several times per month
6. Once per month
7. Can't recall
8. Decline to answer
9. Other: [FREE TEXT]

9. Since your discharge from the Emergency Room on [er_visit_date], have you used anything other than medications to manage your pain?

- a. Yes
- b. No
- c. Do not know

i. If yes, what methods have you used? Please select all that apply.

1. Physical Therapy
2. Chiropractic care
3. Massage
4. Exercise
5. Acupuncture
6. Hot / cold therapy
7. Meditation or Mindfulness
8. Decline to answer

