9. OTHER [FREE TEXT]

10. (Acupuncture Arm Only) Since your discharge from the Emergency Room on [er_visit_date], have you received acupuncture?

- a. Yes
- b. No
- c. Do not know

i. If yes, was the acupuncture effective to relieve your symptoms?

1. Yes
2. No
3. Do not know

11. Since your discharge from the Emergency Room on [er_visit_date], have you experienced new or worsening ILLNESS?

- a. No

b. Yes

IF YES PLEASE DESCRIBE [FREE TEXT]

12. Since your discharge from the Emergency Room on [er_visit_date], have you experienced new or worsening PAIN?

- a. No
- b. Yes
- c. Don't know

IF YES PLEASE DESCRIBE [FREE TEXT]

13. Since your discharge from the Emergency Room on [er_visit_date], have you experienced new or worsening HEALTH ISSUES?

- a. No
- b. Yes
- c. Don't know

IF YES PLEASE DESCRIBE [FREE TEXT]

Instructions: Below are some questions that ask you to rate how you are feeling right now.

SECTION 2 – Pain

1. Please rate your pain, right now, on a scale of 0 to 10, where 0 is no pain, and 10 is the worst pain imaginable.

0 1 2 3 4 5 6 7 8 9 10

SECTION 3 – Anxiety

2. Please rate your anxiety, right now, on a scale of 0 to 10, where 0 is no anxiety, and 10 is the worst anxiety imaginable.

0 1 2 3 4 5 6 7 8 9 10

SECTION 4 – Satisfaction

3. “How satisfied were you with how your pain was managed during your ER visit” on the 5-point Likert scale.

- a. Very Unsatisfied
- b. Somewhat Unsatisfied
- c. Neutral
- d. Somewhat Satisfied
- e. Very Satisfied

4. "Overall how satisfied were you with your treatment during your ER visit?" on the same Likert Scale.
 - a. Very Unsatisfied
 - b. Somewhat Unsatisfied
 - c. Neutral
 - d. Somewhat Satisfied
 - e. Very Satisfied

FOLLOW UP FORM for 1 week F/U (Acupuncture Arm Only, if Post Acupuncture Form Ear Seeds question is "Yes")

SECTION 5 – Ear Seeds

1. Before this follow-up, did you remove the ear seeds that you received in the ER on [er_visit_date]
 - a. Yes
 - i. If yes, when did you remove them? [enter date]
 - b. No (if no, you should remove them now)
2. After your ER discharge, did you ever stimulate/touch the ear seeds yourself for pain relief?
 - a. Yes
 - b. No
3. Any comments on the ear seeds [FREE TEXT]

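### The follow-up form can reveal the arm to a phone caller whom the plan calls blinded, because an acupuncture-arm-only item comes before the pain, anxiety and satisfaction ratings.

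*Combined protocol and SAP*

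**What the plan says.** Section 6.2.4 says of the 1-week visit: "To maintain assessor blinding, any 1-week phone calls (if needed) will be conducted by a research staff (SC or RA) who did not interact" (meaning contact in the ED). Section 6.2.5 says the same of the final visit: "To maintain assessor blinding, any 4-week phone calls (if needed) will be conducted by a research staff (SC or RA) who did not interact" (same meaning). Section 10.2 repeats the no-ED-contact rule for follow-up contacts and says that answers are "collected on paper survey and entered by a member of the research team if the follow-up is completed over the phone".

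Appendix B provides one instrument for both visits, headed "FOLLOW UP FORM for 1 week F/U AND 4 week F/U". Self-completion from an automatic text or email is preferred. Otherwise the "coordinator will text or phone the participant and enter the answers into REDCap".

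Section 1 of that form covers medications and other treatments. Item 9 asks both arms "have you used anything other than medications to manage your pain" and lists acupuncture among the answers. Item 10 is restricted by arm: "Acupuncture Arm Only) Since your discharge from the Emergency Room on [er_visit_date], have you received acupuncture". Pain, anxiety and satisfaction follow as Sections 2, 3 and 4. At 1 week there is a further arm-restricted block on ear seeds, headed "FOLLOW UP FORM for 1 week F/U (Acupuncture Arm Only, if Post Acupuncture Form Ear Seeds question is" yes.

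**The concern.** Keeping ED staff off the telephone protects blinding only if the caller cannot learn the arm in some other way before taking the ratings. An item that applies to one arm, placed ahead of those ratings, supplies that other way.

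Knowing the arm could affect how a caller prompts, probes or records a pain, anxiety or satisfaction score. Two things are at stake. The first is the accuracy of the assessor-blinding statement when the trial is reported. The second is the instrument itself: the primary objective (1.1) is to refine procedures for a fully powered RCT, so a form flaw left in place here could be carried forward.

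A smaller point concerns post-discharge acupuncture. Item 9 lets either arm report it, but only the acupuncture arm gets the direct question and its follow-up on effectiveness, so ascertainment differs by arm.

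**Working it through.** No alpha, power or sample-size figure is involved. The check sets the blinding text beside the order of items on the form.

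**1. What the caller is meant to be blind to.** Section 6.2.3 covers only data collectors in the ED, and only masking to outcomes. Sections 6.1 and 10.2 likewise speak of hiding scores. A telephone caller hears the scores, so that meaning cannot apply. Section 6.2.2 has study staff carry out the randomization in the ED, so excluding staff with ED contact removes the people who know the assignment. Blinding to arm is therefore the sensible reading, although the protocol does not say so explicitly.

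**2. Order of the form at both visits.**

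| Part of the form | Who is asked |
|---|---|
| Section 1: medications; item 9, non-drug methods | Both arms |
| Section 1: item 10, acupuncture since discharge | Acupuncture arm only |
| Section 1: items 11 to 13, new or worsening illness, pain, health issues | Both arms |
| Section 2: pain (1 rating) | Both arms |
| Section 3: anxiety (1 rating) | Both arms |
| Section 4: satisfaction (2 ratings) | Both arms |
| Section 5: ear seeds, 1 week only | Acupuncture arm, if seeds were given |

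**3. How the arm is exposed.** To apply item 10, either REDCap must branch on arm or the caller must already know it. If the item appears, the patient had acupuncture. If it does not, the patient had usual care. Both arms are therefore exposed, and before any rating is taken. Nothing in the protocol hides item 10 from a caller or moves it to the end.

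**4. Carry-over from 1 week to 4 weeks.** Section 6.2.5 excludes only staff who dealt with the patient in the ED. The 1-week caller may therefore also make the 4-week call, already knowing the arm from item 10 or the ear-seed block. The site team description lists a study coordinator and a research assistant, so the pool of callers may be small.

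**5. Count.** Ratings after item 10: 1 pain + 1 anxiety + 2 satisfaction = 4 per phone contact. Over two visits: 4 × 2 = 8 per participant phoned both times. The phone share is not stated, so participants cannot be counted. Purely as an assumption, if 10% to 50% of all 150 were followed up by phone, 0.10 × 150 = 15 to 0.50 × 150 = 75 contacts per visit would be exposed.

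**6. Agreement with the protocol's own lists.** Sections 6.2.4 and 6.2.5 name pain, anxiety and satisfaction before pain medications. The form reverses this. Those lists do not fix an order of administration, but taking the ratings first would agree with them.

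**The case against.** The strongest reply is that little depends on this. The précis labels the trial un-blinded. Recruitment and retention are the primary outcomes in Section 3. Pain and anxiety at 1 and 4 weeks are secondary in 6.1, and the summaries in 9.5 are descriptive. Calls are a fallback, and patients who know their arm give the ratings themselves and may disclose it, for instance under item 9. All of this stands, and it limits the weight of the point. It does not remove it, because disclosure by a patient is incidental whereas an arm-only item exposes the arm whenever the form is followed by phone.

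It can also be said that 10.2 puts phone follow-ups on a paper survey that is not shown and might be ordered differently. That uncertainty is real. However, the Appendix B header has the coordinator phone and enter answers on this form, which is the only version available. Section 2.1 also names paper data collection as a remaining unblinding risk in the earlier multi-site trial and says the present study will fill that gap.

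The reading of blinding as blinding to arm is an interpretation, as step 1 sets out. The remedy is partial, since a 1-week caller still learns the arm at the ear-seed block. It also needs IRB approval, and a change during enrollment alters the context in which ratings are given. The differing questions on post-discharge acupuncture are minor: item 9 captures its use in both arms and no analysis of it is specified.

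**Conclusion.** The concern holds. As laid out, the form lets a caller learn the arm before all four ratings at a phone contact, and the no-ED-contact rule does not prevent this. The conclusion rests on three things: blinding means blinding to arm; phone contacts follow the order in Appendix B; and the paper version does not differ in a way that protects the ratings.

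Only staff-administered phone follow-ups are affected. The size of any bias cannot be estimated, and no primary outcome or sample-size figure changes. The correction should be made because the plan states a property that its own form can defeat, and the remedy is cheap.

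**What to change.** In the REDCap follow-up form and its paper version:

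- Move Sections 2 to 4, with the instruction to rate current feelings, ahead of Section 1.
- Remove the arm restriction from item 10 so that both arms are asked. This also takes its arm cue away from items 11 to 13, which bear on adverse-event reporting under 7.4, and makes the question on post-discharge acupuncture the same in both arms.
- Keep the ear-seed section last, opened only once the scores are saved.
- Where possible, have existing staff who did not make the 1-week call make the 4-week call. Otherwise record whether the caller already knew the arm.
- Record completion mode (self or phone) and, if the form changes during enrollment, the form version.

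In 6.2.4 and 6.2.5, limit the assessor-blinding statement to phone ratings taken by a caller who did not know the arm.

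The cost is one reordered form and its paper copy, one extra question for usual care, two or three short fields, and IRB approval of the modification under 11.1. Recording the form version documents a mid-enrollment change but does not undo its effect on question context. No new staff are needed, since caller rotation is only where possible.

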6.2.5 Completion/Final Evaluation

Four Week Follow-Up Assessment Visit

4 week follow-up Assessment (Follow-up) will be obtained via REDCap based text message or email (or phone call from research staff) at 4 week (+/- 4 days) of patient's ED discharge for both arms. To maintain assessor blinding, any 4-week phone calls (if needed) will be conducted by a research staff (SC or RA) who did not interact with the patient during their study participation in the ED.

- Pain Assessment (Post) using a 0-10 NRS
- Anxiety scores using a 0-10 NRS
- Satisfaction and will be measured through brief questions. All participants will be asked to

answer:

- "How satisfied are you with how your pain was managed during your ED visit" on the 5-point Likert scale.
- "Overall how satisfied are you with your treatment during your ED visit?" on the same Likert Scale.
- Pain medications utilized from ED Discharge to 4 weeks after discharge will be obtained from patients via phone call, email, or text messaging via the secure REDCap electronic data collection tool.

Early Termination

The study doctor or the sponsor can stop a subject's participation at any time without their consent for the following reasons:

- If it appears to be medically harmful to them;
- If they fail to follow directions for participating in the study;
- If it is discovered that they do not meet the study requirements;
- If the study is canceled; or
- For administrative reasons, including competitive enrollment (e.g. the target number of subjects has entered the study.)
- If the patient's clinical condition worsens emergently as determined by the ED physician/clinician.

6.3 Provider Feasibility Assessment

A recruitment email will be sent via REDCap to invite participation. Providers and staff who are interested will click a link to the feasibility study information sheet. Those who wish to participate will click "yes" and be directed to the survey. We will also distribute a recruitment flyer in the ED at each site, inviting ED providers and staff to participate. The flyer will include a QR code that links directly to the study information sheet. Those who wish to participate will click "yes" and be directed to the survey. Feasibility surveys will be completed online by interested participants at their convenience.

- Demographic information including: gender, ethnicity, race, age, how long they have worked in the ED, occupation, contact with the ACUITY study and in what context
- If the provider has ever received acupuncture and if so, how often
- General opinion about acupuncture
 - Do you view acupuncture in general as an appropriate intervention for the ED setting? Likert scale (1-very appropriate—5-Very inappropriate)
 - Do you view acupuncture in general as helpful in managing patient pain in the ED? Likert scale (1-Very helpful—5- Not at all helpful)
- Delivery of ACUITY study in the ED
 - Were you satisfied with how the ACUITY acupuncture intervention was delivered in your setting? Likert scale (1-Very satisfied—5-Very dissatisfied)
 - Did the ACUITY project impose a burden on ED staff in your setting? Not a burden, Somewhat of a burden, Moderate burden, Extreme burden

7. SAFETY ASSESSMENTS

Monitoring of the study for AEs will be continuous throughout the study. In the event of an AE or SAE, it will be reported to the UH IRB in compliance with UH IRB standards.

The investigative team will monitor the data security, data integrity, and patient safety. The study team will meet at least every 2-4 weeks to assess for adherence to protocol and review any safety events. Based on our successful prior experience with our observational study and RCT), the likelihood of

adverse physical, psychological, social, and legal risks is expected to be very small. Acupuncture carries very slight risks for:

- Bleeding,
- Bruising,
- Fainting (acushock)
- Needling pain

In the event a patient experiences an adverse event (AE), they will be treated by providers in the site ED and will have access to emergency response equipment as necessary.

Acupuncture involves inserting thin, sterile needles in the skin. The needles are not inserted into the skin very far. Sometimes the needles cause slight discomfort or minor bleeding. Any acupuncturist who provides treatments in this study will be licensed by the state in which they practice.

7.1 Specification of Safety Parameters

N/A

7.2 Methods and Timing for Assessing, Recording, and Analyzing Safety Parameters

N/A

7.3 Adverse Events and Serious Adverse Events

An adverse event (AE) is any unfavorable and unintended diagnosis, symptom, sign (including an abnormal laboratory finding), syndrome or disease which either occurs during the study, having been absent at baseline, or if present at baseline, appears to worsen. Adverse events are to be recording regardless of their relationship to the study intervention and through follow-up.

A serious adverse event (SAE) is any untoward medical occurrence that results in death, is life threatening, requires inpatient hospitalization or prolongation of existing hospitalization, results in persistent or significant disability/incapacity, or is a congenital anomaly.

7.4 Reporting Procedures

RESPONSIBLE INDIVIDUALS

The site Principal Investigator (PI) is responsible for assessing all AE and SAEs. The site PI will monitor AE reporting and complete the AE PI Report in the ACUITY REDCap for events reported at the 1 and 4 week follow-ups. Research staff are responsible for documenting the events determined to be an AE or SAE, as well as any adverse events occurring in the ED or reported by a subjects physician, in the ACUITY Subject AE Log and reporting these events to the Clinical Coordinating Center within the required timelines.

PROCEDURES

Reporting Adverse Events: The PI or their delegated research staff will review reported events to determine if they qualify as an AE/SAE and assign causality and severity/intensity in REDCap. Research staff will document AE on the Subject ACUITY AE and External AE Summary logs after becoming aware of the event. Subject AE logs will be filed with the individual subject's research files. The External Summary AE log must be provided to the Clinical Coordination Center upon request, including for Quality Assurance, sIRB Continuing Review, and Study Close Out.

Reporting Serious Adverse Events: Research staff will document SAE on the Subject ACUITY AE log after becoming aware of the event. The PI or their delegated research staff will review, sign off on SAE

and assign causality and severity/intensity. If the event satisfies all three of the FDA requirements for reporting SAEs it will be reported to the IRB;

- a. Serious
- b. Unanticipated, and
- c. Related to study product or study procedures

If the event is clarified as an SAE and deemed reportable to the IRB, delegated research staff will report event to the IRB within 5 days of being notified of event via the University Hospital's Cleveland Medical Center's (UHCMC) IRB's "Reportable New information Smart Form" (RNI). If more information becomes available to CIHN regarding SAE, delegated research staff will inform and follow-up with IRB.

